6.4. Immunogenicity analysis

6.4.1. Analysis of immunogenicity planned in the protocol

The analysis of immunogenicity will be performed on the PPS for analysis of immunogenicity and efficacy.

For each study group, at each timepoint that a blood sample result is available:

The percentage of subjects with seropositive levels of anti-CS (proportion of subjects with anti-CS antibody concentrations ≥ 1.9 EU/ml) with 95% CI will be determined at specified blood sampling timepoints in each group (AduFx, 2PedFx, PedFx, Adu2Fx, and Adu1Fx). Anti-CS antibody concentrations will be summarized by GMC. Anti-CS antibody concentrations will be displayed using reverse cumulative curves. Similar analysis will be performed for the anti-full length CS protein (proportion of subjects with anti-CS antibody titres ≥ 200 1/DIL) and anti-C-term antibodies (proportion of subjects with anti-CS antibody concentrations ≥ 100 EPT).

The percentage of subjects with seroprotection levels of anti-HBs (anti-HBs antibody concentrations ≥ 10 mIU/ml) with 95% CI will be determined at specified blood sampling timepoints in each group (AduFx, 2PedFx, PedFx, Adu2Fx, and Adu1Fx). Anti-HBs antibody concentrations will be summarized by GMC. Anti-HBs antibody concentrations will be displayed using reverse cumulative curves.

Anti-CS, anti-full length CS protein and anti-CS avidity index will be summarized by mean, SD, median and quartile and box and whiskers plots will be generated.

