6.6.6. Record information on past hepatitis B immunization

Record information on past hepatitis B immunization in the subject's eCRF, based on best evidences available.

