3.2.2. Immunogenicity

For each vaccination schedule:

- To evaluate anti-CS repeat region antibody response at specified timepoints.
- To evaluate anti-HBs immunoglobulin G (IgG) antibody response at specified timepoints.

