4.2.2. Immunogenicity

- For each vaccination schedule, the immune response to the CS antigen of the investigational vaccine:
 - Anti-CS repeat region antibody concentrations before vaccine administration (Day 0), one month post-Dose 2 (Day 58), six months post-Dose 2 (Day 196), one month post-Dose 3 (Day 226), on the day of challenge (Day 286), 28 days post-challenge (Day 314), and at study end (Day 376) for subjects from AduFx, 2PedFx, PedFx, and Adu2Fx groups and before vaccine administration (Day 0), before Dose 2 (Day 196), one month post-Dose 2 (Day 226), on the day of challenge (Day 286), 28 days post-challenge (Day 314), and at study end (Day 376) for subjects from Adu1Fx group.

- For each vaccination schedule, the immune response to the hepatitis B antigen of the investigational vaccine:
 - Anti-HBs IgG antibody concentrations before vaccine administration (Day 0), one month post-Dose 2 (Day 58), six months post-Dose 2 (Day 196), one month post-Dose 3 (Day 226), on the day of challenge (Day 286), 28 days post-challenge (Day 314), and at study end (Day 376) for subjects from AduFx, 2PedFx, PedFx, and Adu2Fx groups and before vaccine administration (Day 0), before Dose 2 (Day 196), one month post-Dose 2 (Day 226), on the day of challenge (Day 286), 28 days post-challenge (Day 314), and at study end (Day 376) for subjects from Adu1Fx group.

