11.2.4. Immunogenicity

- For a given subject and given immunogenicity measurement, missing or non-evaluatable measurements will not be replaced. Therefore, an analysis will exclude subjects with missing or non-evaluatable measurements.
- The Geometric Mean Concentrations (GMCs) calculations are performed by taking the anti-log of the mean of the log titre transformations. Antibody concentrations below the cut-off of the assay will be given an arbitrary value of half the cut-off of the assay for the purpose of GMC calculation. The cut-off value is defined by the laboratory before the analysis.
- The percentage of subjects seropositive/seroprotected and associated two-sided 95% Clopper-Pearson confidence intervals (CIs) will be computed by vaccine group for each available immunogenicity monitoring.
- A subject seropositive for anti-CS antibody will be a subject whose antibody concentration will be greater than or equal to the cut-off value (anti-CS \geq 1.9 EU/ml).
- Seroprotection rate for anti-HBs antibody is defined as the percentage of subjects with antibody concentration greater than or equal to an established cut-off (anti-HBs \geq 10 mIU/ml).

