Template 4	Summary of study completion with reasons for withdrawal (Intent-to-treat set)	Post-text / Web disclosure	TSL1WITHDRAWAL
Template 4	Summary of study completion with reasons for withdrawal (Per protocol set for analysis of immunogenicity and efficacy for efficacy)	Post-text	TSL1WITHDRAWAL
Template 5	Summary of important protocol deviations leading to elimination (Intent-to-treat set)	In-text / Post-text	TDV1PROTDEV
Template 6	Deviations from protocol for age and intervals between study visits (Intent-to-treat set)	Post-text	TDEVINT1INTVAL
Template 6	Deviations from protocol for age and intervals between study visits (Per protocol set for analysis of immunogenicity and efficacy for efficacy)	Post-text	TDEVINT1INTVAL
Template 10	Exposure to study vaccine (Intent-to-treat set)	In-text / Post-text	TEXOVW1EXPOBYBYVAC
Template 7	Summary of demographic characteristics and baseline characteristics (Intent-to-treat set)	In-text / Post-text	TSL1DEMOG
Template 7	Summary of demographic and baseline characteristics (Per protocol set for analysis of immunogenicity and efficacy for efficacy)	Post-text / in-text/Synopsis	TSL1DEMOG
Template 7	Summary of demographic and baseline characteristics by protection status (Per protocol set for analysis of immunogenicity and efficacy for efficacy)	Post-text	TSL1DEMOG
Template 8	Summary of demographic characteristics and baseline characteristics (Enrolled set)	Web posting	TSL1DEMOG
Template 9	Summary of previous Hepatitis B vaccination (Intent-to-treat set)	Post-text	Specific
Template 9	Summary of previous Hepatitis B vaccination (Per protocol set for analysis of immunogenicity and efficacy for efficacy)	Post-text	Specific
Template 32	Minimum and maximum visit dates (intent-to-treat)	Annex	TACTIV1DATE

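### Post-dose anti-HBs seroprotection and GMC ignore Day 0 anti-HBs status, so they do not isolate the response to the vaccine's hepatitis B antigen

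*SAP*

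**What the plan says.** The secondary objective in SAP 3.2.2 is "To evaluate anti-HBs immunoglobulin G (IgG) antibody response at specified timepoints". SAP 4.2.2 frames the endpoint as the response to the hepatitis B antigen of the vaccine and includes a baseline value: "Anti-HBs IgG antibody concentrations before vaccine administration (Day 0), one month post-Dose 2 (Day 58" and so on.

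The analysis in SAP 6.4.1 (also Protocol 11.9) is by group and timepoint: "The percentage of subjects with seroprotection levels of anti-HBs (anti-HBs antibody concentrations ≥ 10 mIU/ml) with 95% CI will be determined", and "Anti-HBs antibody concentrations will be summarized by GMC", with reverse cumulative curves. SAP 11.2.4 makes seroprotection an absolute status: "Seroprotection rate for anti-HBs antibody is defined as the percentage of subjects with antibody concentration greater than or equal to an established cut-off". It requires no rise from Day 0. The anti-HBs outputs in SAP 12.3 are split by group and by malaria protection status only.

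The hepatitis B exclusion in Protocol 5.3 is HBsAg seropositivity. Neither previous vaccination nor anti-HBs is an exclusion. Protocol 6.6.6 asks sites to "Record information on past hepatitis B immunization in the subject's eCRF, based on best evidences available". The SAP 12.1 table list uses that history in a baseline table, "Summary of previous Hepatitis B vaccination (Intent-to-treat set"), repeated for the per-protocol set.

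**The concern.** Protocol 1.2.2 says the assays are chosen to show whether a fractional dose changes the vaccine-induced response, and it names HBsAg as well as CS. A post-dose percentage at or above 10 mIU/ml answers a different question when some subjects were above 10 before Dose 1: they count as seroprotected whatever the schedule did. The post-dose GMC likewise averages subjects with and without earlier immunity.

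Two consequences follow. Any difference between schedules in subjects below 10 mIU/ml at Day 0 is diluted in the pooled percentage. The pooled GMCs also vary with each group's chance share of previously immune subjects. Allocation does not balance that share by design, because Protocol 6.2.2.2.1 minimises on center only and the study has one center.

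**Working it through.** The documents state no figure for anti-HBs to reproduce; the power figures in Protocol 11.4 concern efficacy.

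**Inputs from the documents.** 26 enrolled per vaccine group and at least 20 challenged, allowing about 20% drop-out (Protocol 11.4; 20/(1 − 0.2) = 25, so 26 suffices). Seroprotection cut-off 10 mIU/ml; assay cut-off 6.2 mIU/ml.

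**Inputs that must be assumed.** The share π already at or above 10 mIU/ml at Day 0, taken as 20% to 80%; that these subjects stay above 10; illustrative post-dose rates of 95% and 70% among the others under two schedules; a post-dose titre ratio F between previously immune and other subjects, the same in both groups.

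**Step 1: dilution of seroprotection.** Pooled rate = π + (1 − π) × rate among those below 10 at Day 0. The difference between two groups with equal π is therefore (1 − π) × the true difference, here 25 points.

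| π | Pooled rates | Difference | Below 10 at Day 0, per 26 (per 20) |
|---|---|---|---|
| 20% | 96% vs 76% | 20 points | 20.8 (16) |
| 40% | 97% vs 82% | 15 points | 15.6 (12) |
| 60% | 98% vs 88% | 10 points | 10.4 (8) |
| 80% | 99% vs 94% | 5 points | 5.2 (4) |

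This occurs even when π is identical in the two groups. Restricting to those below 10 at Day 0 recovers the 25 points, on the numbers in the last column.

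**Step 2: chance imbalance in π.** SD of the difference between two groups = √(2π(1 − π)/n). At π = 50%, n = 20: √(2 × 0.5 × 0.5/20) = 0.158, or 16 points. At π = 20% or 80% it is 12.6 points, and at 40% or 60% it is 15.5; with n = 26 these become 11.1 and 13.6. Over those four values of π, the probability of an imbalance of at least 20 points in one comparison with AduFx is 16% to 26% (n = 20) or 5% to 12% (n = 26). For at least one of the four comparisons it is 43% to 62%, or 17% to 33%.

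**Step 3: effect on the GMC.** The ratio produced by an imbalance d is F^d. At π = 50%, n = 20 and one SD: 10^0.158 = 1.44 for F = 10, 5^0.158 = 1.29 for F = 5, and 30^0.158 = 1.71 for F = 30. At 1.96 SD (0.31) and F = 10: 10^0.31 = 2.0.

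**The case against.** The strongest reply is that the plan is internally sound as description. Seroprotection is a status, correctly computed, and the plan never calls it a response rate. Day 0 is a reported anti-HBs timepoint and vaccination history is tabulated by group, so an imbalance would be visible. The comparisons with AduFx in SAP 12.3 cover anti-CS antibodies and avidity only, and SAP 7 calls all analyses descriptive. Anti-HBs ranks last of the five listed serum assays in Protocol Table 16.

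The GMC effect is also ordinary sampling variation. A 50/50 mixture with a 10-fold gap has a between-subject SD of 0.5 log10. The standard error of a difference between two groups of 20 is then 0.5 × √(2/20) = 0.158 log10, a ratio of 1.44. That is the figure in Step 3, and this variability is already inside the planned 95% intervals.

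All of this stands. A reader might infer that differences between schedules will reflect earlier hepatitis B vaccination, or that imbalance could outweigh any schedule effect. The documents support neither: the five vaccine groups are randomised, so prior immunity is balanced in expectation, and no anti-HBs schedule effect, prevalence or titre gap is given against which to judge the noise.

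What the reply does not remove is the dilution, which randomisation leaves untouched. Separate baseline and post-dose tables also do not give a reader the post-dose result among those below 10 at Day 0; that needs the cross-classification. Descriptive status is not a full answer either, since Protocol 11.11 says the evaluations between schedules aim to characterise the difference in immunogenicity.

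**Conclusion.** The point holds as a limited gap in a secondary endpoint. The post-dose anti-HBs percentage and GMC, as planned, do not separate vaccine-induced response from immunity present before Dose 1. The seroprotection difference is diluted by (1 − π), provided already-immune subjects stay above 10 mIU/ml. The GMCs remain valid but less precise than they could be: the noise is about a 1.4-fold ratio at one SD under 50% prior immunity, a 10-fold gap and 20 per group, or 1.3 to 1.7 for gaps of 5- to 30-fold. Every prevalence and fold value here is an assumption. There is no systematic confounding of schedule, no planned formal anti-HBs comparison is affected, and primary efficacy is untouched.

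One related label should be reconciled: Protocol Tables 15 and 17 name the hepatitis B screening test as surface antibody, whereas the exclusion criterion concerns HBsAg. No anti-HBs exclusion is stated, so eligibility of previously vaccinated adults is read from the criterion.

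**What to change.** Keep the existing anti-HBs tables. Add to SAP 6.4.1 and the SAP 12.3 table list:

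- Anti-HBs seroprotection and GMC by schedule and timepoint, split by Day 0 status (<10 versus ≥10 mIU/ml), with post-dose seroprotection interpreted as a response to the vaccine only in those <10 at Day 0.
- A supportive GMC by schedule from a model of log10 titre adjusted for log10 Day 0 titre.
- Recorded hepatitis B vaccination history alongside, because previously vaccinated subjects whose titres have waned below 10 would otherwise look naive.

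All the data are already collected. The cost is a few extra tables and one simple model. The strata will be small (Step 1) with wide intervals. Day 0 values below the assay cut-off are all set to half of it (6.2/2 = 3.1 mIU/ml), so the covariate will have a cluster at one value, which is a reason to keep the adjusted GMC supportive.

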6.4.2. Additional considerations

In addition to the previous analyses, the immunogenicity analyses will be performed per protection status (P and NP) overall (pooled vaccine groups) and within each vaccine group.

A comparisons of the log-transformed means of anti-CS antibodies (repeated, full length, C-Term and avidity index) post vaccination and at the time of the challenge and for P vs NP (Student 2-Sample Test) will be performed.

Exploratory analyses using logistic regression models will be evaluated to describe the relationship between immune read outs and the probability of infection (P vs NP).

Explanatory variables will include all or a part of available immune read outs at time of analysis (anti-CS, anti-full length CS protein, avidity index).

In a first step, immune responses will be plotted by group and protection status as well as cross-tabulated to understand potential correlation structures. Then, relevant models will be constructed to evaluate what are the independent predictors of protection, both pooled over the treatment groups (is/are there a generic driver(s)?) and by treatment schedule/including interactions (is protection mediated through different mechanisms between schedules?).

6.5. Analysis of safety

6.5.1. Analysis of safety planned in the protocol

The analysis of safety will be performed on the ITTS.

The percentage of subjects with at least one local AE (solicited and unsolicited), with at least one general AE (solicited and unsolicited) and with any AE during the 7-day or 30-day follow-up period after each vaccine dose and overall will be tabulated with exact 95% CI. The percentage of doses followed by at least one local AE (solicited and unsolicited), by at least one general AE (solicited and unsolicited) and by any AE during the 7-day or 30-day follow-up period will be tabulated with exact 95% CI. The same computations will be done for Grade 3 AEs, for any AEs considered related to vaccination and for any Grade 3 AEs considered related to vaccination.

The percentage of subjects reporting each individual solicited local AE (any grade and Grade 3) and each individual solicited general AE (any grade, Grade 3, any related, Grade 3 related, resulting in medically attended visit) during the 7-day follow-up period (Day 0-6) after each vaccine dose and overall will be tabulated for each group. Similarly, the percentage of doses followed by each individual solicited local and general AE will be tabulated, for the overall and for each vaccination course, with exact 95% CI.

For fever (fever is defined as temperature $\geq 37.5^{\circ}\text{C}/99.5^{\circ}\text{F}$ for oral, axillary or tympanic route, or $\geq 38.0^{\circ}\text{C}/100.4^{\circ}\text{F}$ for rectal route), the number and percentage of subjects reporting fever by half degree ($^{\circ}\text{C}$) cumulative increments during the first seven days (Day 0-6) after each vaccine dose and overall will be tabulated. Similar tabulations will be performed for any fever with a causal relationship to vaccination and Grade 3 ($> 39.0^{\circ}\text{C}$) causally related fever. The maximum temperature reported over the 7-day follow-up period (Day 0-6) overall doses will be tabulated.

The percentage of subjects reporting unsolicited AEs within 30 days (Day 0-29) after each vaccine dose (overall doses) and percentage of subjects reporting AEs after the sporozoite challenge will be tabulated by group and by MedDRA preferred term with exact 95% CI. Similar tabulation will be done for Grade 3 unsolicited AEs, for any causally related unsolicited AEs and for Grade 3 causally related unsolicited AEs.

The percentage of subjects reporting SAEs (all, fatal, related) occurring within 30 days (day of vaccination and 29 subsequent days) after each dose of study vaccine, classified by the MedDRA preferred term level will be tabulated with exact 95% CI.

The percentage of subjects reporting SAEs (all, fatal, related) occurring from Dose 1 (Day 0) until last study visit (Day 376), classified by the MedDRA preferred term level will be tabulated with exact 95% CI.

The percentage of subjects reporting SAEs (all, fatal, related) occurring from day of challenge (Day 286) to the end of the challenge phase (Day 314), according to the MedDRA classification will be tabulated with exact 95% CI.

Subjects reporting pregnancies will be described.

The percentage of subjects reporting an AE or SAE leading to withdrawal from further vaccination from Dose 1 (Day 0) until last study visit (Day 376), classified by MedDRA preferred term level, will be tabulated with exact 95% CI.

The percentage of vaccinated subjects reporting AEs of specific interest (meningitis and pIMDs) from Dose 1 (Day 0) until last study visit (Day 376), classified by MedDRA preferred term level, will be tabulated with exact 95% CI.

Biochemistry (ALT, AST and creatinine) and hematological (hemoglobin, WBC and platelets) laboratory values will be presented by visit according to toxicity grading scales and tabulated by group.

The normal ranges and toxicity grading for laboratory safety parameters used in this study are presented in [Table 4](#)

Table 4 Toxicity grading scales for blood testing

Adverse event	Intensity grade	Intensity*
Hemoglobin (males)	Normal range	≥12.5 g/dl
	1	< 12.5 but ≥ 11.0 g/dl
	2	< 11.0 but ≥ 10.0 g/dl
	3	< 10.0 g/dl
Hemoglobin (females)	Normal range	≥11.5 g/dl
	1	< 11.5 but ≥ 10.5 g/dl
	2	< 10.5 but ≥ 9.5 g/dl
	3	< 9.5 g/dl
Increase in leukocytes (WBC)	Normal range	≤10799 cells/mm ³
	1	10800 - 15000 cells/mm ³
	2	15001 - 20000 cells/mm ³
	3	> 20001 cells/mm ³
Decrease in leukocytes (WBC)	Normal range	≥3200 cells/mm ³
	1	2500 - 3199 cells/mm ³
	2	1500 - 2499 cells/mm ³
	3	< 1500 cells/mm ³
Decrease in platelets	Normal	≥140000 cells/mm ³
	1	125000 - 139000 cells/mm ³
	2	100000 - 124000 cells/mm ³
	3	< 100000 cells/mm ³
Alanine Aminotransferase	Normal range	Below ULN (60 U/l for males; 40 U/l for females)
	1	1.1 - 2.5 x ULN
	2	2.6 - 5 x ULN
	3	> 5 x ULN
Aspartate Aminotransferase	Normal range	Below ULN (40 U/l for males; 35 U/l for females)
	1	1.1 - 2.5 x ULN
	2	2.6 - 5 x ULN
	3	> 5 x ULN
Creatinine (males)	Normal range	≤1.39 mg/dl
	1	1.4 - 1.79 mg/dl
	2	1.8 - 2.0 mg/dl
	3	> 2.0 mg/dl
Creatinine (females)	Normal range	≤1.29 mg/dl
	1	1.3 - 1.69 mg/dl
	2	1.7 - 1.9 mg/dl
	3	>1.9 mg/dl

ULN: upper limit of normal range

* Grading scale adapted from [FDA guidance for industry toxicity grading scale for healthy adult and adolescent volunteers enrolled in preventive vaccine clinical trials (September 2007)].

The percentage of subjects using concomitant medication (any medication, any antipyretic and any prophylactic medication, respectively) during the 7-day follow-up period (Day 0-6) after vaccination will be summarized by group after each dose and overall. The percentage of subjects using concomitant medication during the entire sporozoite challenge (D286-314) will be summarized by group.

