11.10. Analysis of safety

The analysis of safety will be performed on the TVC.

The percentage of subjects with at least one local AE (solicited and unsolicited), with at least one general AE (solicited and unsolicited) and with any AE during the 7-day or 30-day follow-up period after each vaccine dose and overall will be tabulated with exact 95% CI. The percentage of doses followed by at least one local AE (solicited and unsolicited), by at least one general AE (solicited and unsolicited) and by any AE during the 7-day or 30-day follow-up period will be tabulated with exact 95% CI. The same computations will be done for Grade 3 AEs, for any AEs considered related to vaccination and for any Grade 3 AEs considered related to vaccination.

The percentage of subjects reporting each individual solicited local AE (any grade and Grade 3) and solicited general AE (any grade, Grade 3, any related, Grade 3 related, resulting in medically attended visit) during the 7-day follow-up period (Day 0-6) after each vaccine dose and overall will be tabulated for each group. Similarly, the percentage of doses followed by each individual solicited local and general AE will be tabulated, overall vaccination course, with exact 95% CI.

For fever, the number and percentage of subjects reporting fever by half degree ($^{\circ}\text{C}$) cumulative increments during the first seven days (Day 0-6) after each vaccine dose and overall will be tabulated. Similar tabulations will be performed for any fever with a causal relationship to vaccination and Grade 3 ($> 39.5^{\circ}\text{C}$) causally related fever.

The percentage of subjects reporting unsolicited AEs within 30 days (Day 0-29) after each vaccine dose (overall doses) and percentage of subjects reporting AEs after the sporozoite challenge will be tabulated by group and by MedDRA preferred term with exact 95% CI. Similar tabulation will be done for Grade 3 unsolicited AEs, for any causally related unsolicited AEs and for Grade 3 causally related unsolicited AEs.

The percentage of subjects reporting SAEs and pregnancies will be described in detail.

The percentage of vaccinated subjects reporting AEs of specific interest (meningitis and pIMDs) will be described in detail.

Biochemistry (ALT, AST and creatinine) and hematological (hemoglobin, WBC and platelets) laboratory values will be presented according to toxicity grading scales and tabulated by group.

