11. ANNEX 1 STANDARD DATA DERIVATION RULE AND STATISTICAL METHODS

11.1. Statistical Method References

The exact two-sided 95% CIs for a proportion within a group will be the Clopper-Pearson exact CI [Clopper CJ, Pearson ES. The use of confidence or fiducial limits illustrated in the case of binomial. *Biometrika*. 1934;26:404-413].

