11.2.2. Dose number

- The study dose number is defined in reference to the number of study visits at which vaccination occurred. More specifically dose 1 refers to all vaccines administered at the first vaccination visit while dose 2 corresponds to all vaccinations administered at the second vaccination visit even if this is the first time a product is administered to the subject.
- Relative dose: the relative dose for an event (AE, medication, vaccination) is the most recent study dose given before an event. In case the event takes place on the day a study dose is given, the related dose will be that of the study dose, even if the event actually took place before vaccination. For instance, if an AE begins on the day of the study vaccination but prior to administration of the vaccine, it will be assigned to this dose. In case a study dose is not administered (eg dose 2) and an event occurs after the subsequent study dose (eg 3rd study dose), the relative dose of the event will be study dose associated to the subsequent study dose (eg dose 3).
- The number of doses for a product is the number of times the product was administered to a subject.
- The incidence per dose is the number of vaccination visits at which an event was reported among all vaccination visits.

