Note that for all tables described in this section, the way the percentage of subjects will be derived will depend on the event analysed (see table below for details). As a result, the N value will differ from one table to another.

Event	N used for deriving % per subject for Vaccination phase	N used for deriving % per dose for Vaccination phase
Concomitant vaccination	All subjects with study vaccine administered	All study visits with study vaccine administered
Solicited general symptom	All subjects with at least one solicited general symptom documented as either present or absent (i.e., symptom screen completed)	All study visits with study vaccine administered and with at least one solicited general symptom documented as either present or absent (i.e., symptom screen completed)
Solicited local symptom	All subjects with at least one solicited local symptom documented as either present or absent (i.e., symptom screen completed)	All study visits with study vaccine administered and with at least one solicited local symptom documented as either present or absent (i.e., symptom screen completed)
Unsolicited symptom	All subjects with study vaccine administered	All study visits with study vaccine administered
Concomitant medication	All subjects with study vaccine administered	All study visits with study vaccine administered

- Related dose: The related dose for an event (e.g., AE, medication, vaccination,...) is the study dose given before an event. In case the event takes place on a day a study dose is given, if the investigator has indicated the timing (before or after the vaccination) the related dose for this event is the most recent study dose given before this event. If the investigator has not indicated the timing, the related dose will be that of the study dose even if the event actually took place before.

Number of decimals displayed:

The following decimal description from the decision rules will be used for demography, efficacy, immunogenicity and safety/reactogenicity results.

Display Table	Parameters	Number of decimal digits
Demographic characteristics	Mean, median age	1
Demographic characteristics	SD (age)	1
Reactogenicity	Mean, Min, Q1, Median, Q3, Max for duration	1
All summaries	p-value	3

Percentages and their corresponding confidence limits will be displayed with:

- no decimals when there are fewer than 50 subjects in each tabulated group
- one decimal when there are at least 50 subjects in at least one tabulated group

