12.6.4. Reactogenicity and safety

Template 19 Compliance in completing solicited adverse events information (intent-to-treat)

		<Group 1>		<Group 2>		Compliance (%)
		N	n	N	n	
		Compliance (%)		Compliance (%)		
<Vaccination at visit 1>	General solicited adverse events	xxx	xx.x	xxx	xxx	xx.x
		xxx	xx.x	xxx	xxx	xx.x
	Local solicited adverse events	xxx	xx.x	xxx	xxx	xx.x
<Vaccination at visit X>	General solicited adverse events	xxx	xx.x	xxx	xxx	xx.x
		xxx	xx.x	xxx	xxx	xx.x
	Local solicited adverse events	xxx	xx.x	xxx	xxx	xx.x
...		xxx	xx.x	xxx	xxx	xx.x
Per vaccination	...		xx.x	xxx	xxx	xx.x
	General solicited adverse events	xxx				
		xxx				
	Local solicited adverse events	xxx				
		xxx				

Template 20 Incidence and nature of symptoms (solicited and unsolicited) within 7-day following each vaccination and overall (Intention-to-treat set)

	<Group 1>				<Group 2>			
	n	%	95% CI		n	%	95% CI	
			LL	UL			LL	UL
<Vaccination at visit 1> N	xxx				xxx			
Any symptom	xxx	xx.x	xx.x	xx.x	xxx	xx.x	xx.x	xx.x
Local symptom	xxx	xx.x	xx.x	xx.x	xxx	xx.x	xx.x	xx.x
General symptom	xxx	xx.x	xx.x	xx.x	xxx	xx.x	xx.x	xx.x

<Vaccination at visit 2> ...

...

Per subject

Per vaccination

For each dose and overall/subject:

N= number of subjects with at least one administered dose

n/%= number/percentage of subjects presenting at least one type of symptom whatever the study vaccine administered

For overall/dose:

N= number of administered doses

n/%= number/percentage of doses followed by at least one type of symptom whatever the study vaccine administered

95% CI = exact 95% confidence interval, LL = Lower Limit, UL = Upper Limit

Template 21 Incidence of solicited <local/general> symptoms within 7-day following each vaccination and overall (Intention-to-treat set)

Symptom: Xxxxx

	<Group 1>				<Group 2>			
	n	%	95% CI		n	%	95% CI	
			LL	UL			LL	UL
<Vaccination at visit 1> N	xxx				xxx			
Any	xxx	xx.x	xx.x	xx.x	xxx	xx.x	xx.x	xx.x
Related	xxx	xx.x	xx.x	xx.x	xxx	xx.x	xx.x	xx.x
Grade 3	xxx	xx.x	xx.x	xx.x	xxx	xx.x	xx.x	xx.x
Grade 3 related	xxx	xx.x	xx.x	xx.x	xxx	xx.x	xx.x	xx.x
Medically attended visit								

<Vaccination at visit 2> ...

...

Per subject

Per vaccination

For each dose and overall/subject:

N= number of subjects with at least one administered dose

n/%= number/percentage of subjects reporting at least once the symptom

For Overall/dose:

N= number of administered doses

n/%= number/percentage of doses followed by at least one type of symptom

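### The pooled per-dose AE rows carry an interval labelled exact that counts two or three doses of one subject as independent; its true coverage is unknown and may fall below 95%

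*SAP*

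**What the plan says.** Protocol 11.10 plans that "the percentage of doses followed by each individual solicited local and general AE will be tabulated, overall vaccination course, with exact 95% CI". SAP 6.5.1 repeats this and extends it to single vaccinations: "doses followed by each individual solicited local and general AE will be tabulated, for the overall and for each vaccination course, with exact 95% CI". The same section plans per-dose percentages with exact intervals for any, local and general AEs, for Grade 3 AEs and for related AEs.

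SAP 11.1 fixes the method: "The exact two-sided 95% CIs for a proportion within a group will be the Clopper-Pearson exact CI". SAP 11.2.2 fixes the unit: "The incidence per dose is the number of vaccination visits at which an event was reported among all vaccination visits". The footnotes to Templates 20 and 21 (SAP 12.6.4) give "N= number of administered doses" for the overall/dose rows. The denominator table in SAP 11.2.5 restricts solicited general symptoms to "All study visits with study vaccine administered and with at least one solicited general symptom documented as either present or absent". The two denominators are not identical, but both count doses. Templates 22 and 30 have the same per-vaccination row with 95% limits.

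The companion rows in Templates 20 and 21 count people: "N= number of subjects with at least one administered dose". Neither document mentions clustering, a design effect, GEE or a bootstrap for the dose-level rows. SAP section 7 calls all analyses descriptive.

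**The concern.** Subjects, not doses, are randomised. Clopper-Pearson has its guaranteed coverage only when the count is a sum of independent trials sharing one probability. The pooled rows depart from that in two ways:

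- A subject contributes two or three doses, and someone who reacts to one dose may well react to the next. Positive correlation inflates the variance of the pooled percentage.
- Every vaccine arm mixes full and 1/5th doses (Protocol 1.2.2), so the event probability need not be constant. Unequal rates within a subject reduce the variance relative to the binomial.

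The two effects pull in opposite directions, and the plan estimates neither. What is at stake is the stated precision of reactogenicity by schedule, a secondary objective. The 7-day AE summary (Template 20) goes to the in-text tables and synopsis, and the solicited-symptom tables (Template 21) go to web disclosure. The pooled rows stand there beside per-subject rows, and nothing tells the reader that only one of the two has the coverage claimed.

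**Working it through.** The documents state no per-dose interval or within-subject correlation, so there is no planned figure to reproduce.

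**Inputs from the documents.** 26 subjects per vaccine arm (Protocol 11.4). Four arms on a 0, 1, 7-month schedule and one on 0, 7 months (Protocol 1.2.2). Doses per full arm: 26 × 3 = 78, and 26 × 2 = 52 in Adu1Fx. Clopper-Pearson, 95%, two-sided (SAP 11.1).

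**Assumed.** The correlation ρ between doses of one subject, and the event rates by dose.

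**1. Interval width with equal dose rates.** Design effect D = 1 + (m − 1)ρ, where m is doses per subject. Effective number of doses = doses / D.

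| Arm | Planned 95% CI | ρ = 0.1 | ρ = 0.3 | ρ = 0.5 |
|---|---|---|---|---|
| 39/78 doses (m = 3) | 38.5-61.5% | 37.3-62.7% | 35.3-64.7% | 33.6-66.4% |
| 26/52 doses (m = 2) | 35.8-64.2% | 35.1-64.9% | 33.8-66.2% | 32.6-67.4% |

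The planned width is 91%, 79% and 70% of that needed with three doses, and 95%, 88% and 82% with two.

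**2. Actual non-coverage with equal dose rates.** The distribution of the total over 26 subjects was enumerated under a beta-binomial model, with true rates of 10%, 30%, 50% and 80%. For three doses:

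| ρ | Non-coverage of the nominal 95% CI |
|---|---|
| 0 | 3.1-4.7% |
| 0.2 | 6.8-9.4% |
| 0.3 | 8.9-11.8% |
| 0.5 | 12.8-16.2% |

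For two doses at ρ = 0.5 it is 5.1-8.9%. Averaged over true rates of 5-95%, coverage at ρ = 0 is 96.4% (three doses) and 96.7% (two). This slack absorbs a ρ of roughly 0.1 with three doses and 0.2 with two.

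**3. Unequal dose rates.** Logistic-normal model with between-subject SD 1.0 on the logit scale. The variance ratio is actual over binomial variance.

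| Rates by dose (assumed) | Variance ratio | Coverage |
|---|---|---|
| 80/80/50% | 1.16 | 93.5% |
| 80/80/30% | 0.95 | 97.0% |
| 80/50% | 1.03 | 95.6% |
| 80/30% | 0.84 | 97.7% |

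At SD 2.0, coverage is 89.6% for 80/80/50% and 94.9% for 80/80/30%. A latent-normal model agrees: 80/80/50% gives 9.3% non-coverage at a binary correlation of 0.29, whereas 80/20/20% (a possible pattern for Adu2Fx) stays at 1.5-4.4% up to 0.31.

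**4. What a clustered interval looks like.** For 23/78 doses (29%), the planned interval is 19.7-40.9%. With D = 2.0 and a t correction on 25 df, effective N = 78/2.0 × (1.96/2.06)² = 35.3, which gives 15.4-47.2%. Widths are 31.8 against 21.2 points, a ratio of 1.5. D = 2.0 is ρ = 0.5 with equal rates, so this is an unfavourable case and not a typical one.

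**The case against.** The strongest reply is that the direction of the error is not established. A reader might infer that the per-dose intervals simply are too narrow. The documents do not support that: they give no correlation, Clopper-Pearson starts out conservative, and the mix of full and 1/5th doses can cancel the effect of clustering or reverse it. The equal-rate figures describe one corner of what could happen. This objection stands, and the point is limited accordingly.

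A second reply is that little depends on these rows. The safety endpoint is occurrence after each vaccination. The by-vaccination rows answer it with one dose per subject and the per-subject rows summarise it, and both are valid as planned. The templates concerned contain no p-value or between-arm contrast, and SAP section 7 calls everything descriptive. This also stands and sets the weight of the point. It does not rescue the interval, because showing precision is the only purpose of a descriptive interval.

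Third, an estimated design effect is undefined at 0% or 100% and unstable with one or two events, as may occur in the Grade 3 rows. That is correct, and any clustered interval needs a rule for it. Little is lost by omitting the interval there: at a 2% rate the planned one has non-coverage of only 2.2-3.7% for correlations up to 0.16.

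**Conclusion.** The point holds as a minor one. In the pooled per-dose rows the label exact is not justified, and the true coverage depends on a correlation and a dose-rate pattern that the plan neither states nor estimates. With three doses and assumed equal rates of 10-80%, non-coverage is about 7-9% at correlation 0.2 and 13-16% at 0.5. With small correlation, or full and fractional doses that differ strongly, it is at or below the nominal 5%. For the same correlation and similar rates, the three-dose arms are affected more than Adu1Fx.

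Two stronger readings should be avoided. One is that the Adu1Fx interval is itself too wide. Under positive correlation with equal rates it is affected in the same direction as the others, only less, so any distortion is relative to the three-dose arms. The other is that the safety or efficacy conclusions are compromised. The by-vaccination rows, the per-subject rows and the Fisher and log-rank comparisons use one observation or outcome per subject and are untouched.

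**What to change.** In SAP 6.5.1 and 11.1, and in the per-vaccination rows of Templates 20, 21, 22 and 30, keep the per-dose percentages and replace Clopper-Pearson with an interval clustered on subject. One workable form is Clopper-Pearson at an effective number of doses:

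- estimate the design effect from the between-subject variance in that row, which captures both the correlation and the dose mix;
- apply a t correction on the number of evaluable subjects minus 1;
- cap the effective number at the actual number of doses.

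In latent-normal simulations that included unequal dose rates, this held non-coverage at 1.7-6.8%. Where the design effect cannot be estimated (0% or 100%), or events fall below a small count fixed in the SAP beforehand, print the percentage without a CI. Keep Clopper-Pearson for all by-vaccination and per-subject rows.

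The simpler alternative is to drop the CI from all pooled per-dose rows and let the per-subject rows show precision.

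The cost is one sentence in the SAP and a small change to the table macro, with no new data or subjects. The downside is that the intervals will usually be somewhat wider and will depart from the sponsor's standard template.
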